### **Permitted Medications/Non-Medications**

Medications to treat any AEs the subject experiences during the study are permitted at the Investigator's discretion and/or in consultation with the Medical Monitor. Intermittent use of acetaminophen at doses of  $\leq 2$  g/day or ibuprofen  $\leq 1200$  mg/day is allowed throughout the study. Hormonal contraceptives are permitted throughout the study.

### **Meals and Dietary Restrictions/Dosing Under Fasting Conditions**

Subjects will fast overnight for at least 8 hours prior to dosing on Day 1. Subjects will remain fasted until at minimum 4 hours after dosing, at which time lunch may be consumed. Other meals will be supplied at appropriate times thereafter while subjects are resident in the unit.

### **Food Impact Evaluation Under Fed Conditions**

Subjects will fast overnight for at least 8 hours prior to the start of a high-fat, high-calorie meal which will be entirely consumed in less than 30 minutes. The dose of VT-1598 will be administered 30 minutes after the start of the meal (defined as the time when the first bite of the

meal is taken) with 8 ounces (240 mL) of water. The high-fat, high-calorie test meal will be comprised of a breakfast of approximately 900-1000 calories, with approximately 150 calories from protein, 250 calories from carbohydrates, and 500-600 calories from fat (an example of a high-fat, high-calorie breakfast is: 2 eggs fried in butter, 2 strips of bacon, 2 slices of toast with butter, 4 ounces of hash brown potatoes fried with butter and 8 ounces or 240 mL of whole milk). No other food will be ingested until after a minimum of 4 hours after dosing, at which time lunch may be consumed. Water can be allowed as desired except for one hour before and after drug administration. Other meals will be supplied at appropriate times thereafter while subjects are resident in the unit.

### **Exercise**

Subjects will be prohibited from engaging in strenuous activity within 48 hours prior to dosing and should be discouraged from engaging in strenuous activity within 48 hours prior to returning to the CRU on Days 7, 14, and 21. Subjects will not engage in strenuous activity at any time during the confinement period. Walking at a normal pace will be permitted.

#### **7.1.3 Assessment of Subject Compliance with Study Intervention/Investigational Product/Investigational Device**

Subjects will be directly observed at the time of dosing by a member of the clinical research team who is licensed to administer the study product. Study personnel will examine the oral cavity of each subject following each dose to assure that all study product was swallowed. Administration will be documented and entered into the eCRF.

## **7.2 Laboratory Evaluations**

### **7.2.1 Clinical Laboratory Evaluations**

All laboratory assessments will be done by the clinical site's certified laboratory. Laboratory toxicity grading will be determined by use of the FDA Guidance for Industry: Toxicity Grading Scale for Healthy Adult and Adolescent Volunteers Enrolled in Preventive Vaccine Clinical Trials September 2007 and the Division of Microbiology and Infectious Diseases (DMID) Adult Toxicity Table November 2007, as modified for this study and appropriate for the administration of VT-1598 ([Appendix B](#) VT-1598 Toxicity Grading Criteria for Normal Human Subjects).

At Screening and at baseline, laboratory test values that fall outside the reference range on the laboratory reports and deemed not clinically significant by the Investigator may be repeated at the discretion of the Investigator (to assess for transitional conditions). A laboratory value that is Grade 1 (with the exception of ALT, AST, Total bilirubin, hemoglobin or serum creatinine) will be allowed if not considered to be clinically significant by the investigator

---

If a single repeat Screening evaluation or baseline is within the reference range, the subject may be further considered for study eligibility **Note:** Hematuria during active menses causing urinalysis results outside the reference range will not be considered clinically significant (not an AE). Post-dose serum cortisol levels Grade 2 or greater must be repeated and if confirmed, then an ACTH stimulation test should be performed.

\*See [Appendix B](#) VT-1598 Toxicity Grading Criteria for Normal Human Subjects.

### **Pregnancy Testing**

All women of childbearing potential must undergo serum pregnancy testing at Screening and Baseline to assess protocol eligibility. Serum pregnancy tests will be performed thereafter as specified in the Schedule of Assessments and Procedures. [Appendix A](#) VT-1598 Schedule of Study Procedures and Evaluations

Female subjects reporting as post-menopausal must undergo testing for serum FSH levels to assess childbearing potential at Screening.

### **Immunology**

All subjects must undergo testing for the detection of antibodies to HIV-1 and HIV-2, HBsAg, and antibodies to HCV at Screening to assess protocol eligibility.

### **Clinical Chemistry Panel**

All subjects must undergo clinical chemistry testing (albumin, glucose, blood urea nitrogen or urea, potassium, calcium, sodium, chloride, total protein, creatinine, triglycerides, total cholesterol, low-density lipoprotein cholesterol, high-density lipoprotein cholesterol, total carbon dioxide, creatine phosphokinase, phosphorus, magnesium, gamma-glutamyl transferase (GGT), alkaline phosphatase, AST, ALT, total bilirubin, direct bilirubin and serum cortisol) at Screening and Baseline to assess protocol eligibility. Clinical chemistry tests will be performed thereafter as specified in the [Appendix A](#) Schedule of Assessments and Procedures. Subjects must fast a minimum of 8 hours before blood collection for a clinical chemistry panel. Serum cortisol levels must be drawn prior to 10 a.m.

### **Hematology and Coagulation**

All subjects must undergo hematology (red blood cell count, total and differential white blood cell counts, hemoglobin, hematocrit, and platelet count) and coagulation (activated partial thromboplastin time, prothrombin time, and international normalized ratio) testing at Screening and Baseline to assess protocol eligibility. Hematology and coagulation tests will be performed thereafter as specified in the [Appendix A](#) Schedule of Assessments and Procedures.

## Urinalysis

All subjects must undergo urinalysis testing (leukocyte esterase, blood, pH, and specific gravity [microscopic tests to be completed if dipstick urinalysis is abnormal]) at Screening and Baseline to assess protocol eligibility. Urinalysis testing will be performed thereafter as specified in the [Appendix A](#) Schedule of Assessments and Procedures.

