## 2.3 Potential Risks and Benefits

### 2.3.1 Potential Risks

As VT-1598 has not yet been studied in humans, no information is currently available regarding AEs associated with its use.

When oral VT-1598 was evaluated in general toxicity studies in rats and monkeys, the following side effects were noted:

- slight decreases in body temperature and heart rate
- minimal to mild increases in serum cholesterol
- decreases in mean body weight and food consumption
- decreases in lymphocyte and eosinophil counts and/or increases in monocyte counts
- moderate to marked prolongations of APTT and prothrombin times
- minimal to mild decreases in alkaline phosphatase
- mild to moderate decreases in serum albumin
- mild decrease in serum creatinine
- mild to moderate, dose-dependent increases in gamma-glutamyl transferase (GGT)
- mild to moderate decreases in urine pH and specific gravity
- mild increase in urine volume.

Among the currently-available azole antifungal agents, numerous clinically-significant drug interactions have been identified. Most of these interactions are a result of competitive inhibition of liver oxidative metabolism via reversible binding to CYP enzymes. Azoles interfere mainly with CYP3A4, CYP2C9, and CYP2C19 characterized by individual affinity and they therefore exhibit slightly different drug interaction profiles. In addition, itraconazole, posaconazole and isavuconazole are inhibitors of gastric P-glycoprotein, which limits systemic exposure to many drugs by inhibiting gastrointestinal absorption.

Adverse effects of the currently-available azole antifungals vary across the individual agents and are described in the following paragraphs:

**Fluconazole:** Fluconazole is generally well tolerated and serious adverse events (SAEs), mainly hepatotoxicity, are rare. Gastrointestinal disturbances are the most common complaints. High doses (400-800 mg/day) of fluconazole may be associated with a rare and distinct set of birth defects in infants whose mothers were treated with the drug during the first trimester of pregnancy. The US Food and Drug Administration (FDA) is evaluating the results of a Danish study that concluded there is a possible increased risk of miscarriage with the use of oral fluconazole for yeast infections.

---

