h Clinical laboratory tests to include: clinical chemistry panel (albumin, glucose, blood urea nitrogen or urea, potassium, calcium, sodium, chloride, total protein, creatinine, triglycerides, total cholesterol, low-density lipoprotein cholesterol, high-density lipoprotein cholesterol, total carbon dioxide, creatine phosphokinase, phosphorus, alkaline phosphatase, aspartate aminotransferase, alanine aminotransferase, total bilirubin, direct bilirubin, magnesium, gamma-glutamyl transferase (GGT) and serum cortisol), CBC (red blood cell count, total and differential white blood cell count, hemoglobin, hematocrit, and platelet count), coagulation parameters (activated partial thromboplastin time, prothrombin time, and international normalized ratio), and urinalysis (leukocyte esterase, blood, pH, and specific gravity [microscopic tests to be completed if dipstick urinalysis is abnormal]). Subjects must fast at least 8 hours before blood collection for the clinical chemistry panel. Cortisol must be fasting and drawn before 10 a.m.

i Serum pregnancy test for women of childbearing potential at Screening, Day -1 and Day 21 (Final Study Visit).

---

j Follicle-stimulating hormone on all post-menopausal women at Screening.

k Urine drug test at Screening and on Day -1 to include cotinine, opiates, cocaine, cannabinoids, phencyclidine, benzodiazepines, barbiturates, amphetamines, and cotinine. Alcohol screen is performed by urine test.

l Immunology screen to include tests for the detection of antibodies to HIV-1 and HIV-2, HBsAg, and antibodies to HCV.

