WBC Decrease – cell/mm 	2,500– 3,999	1,500 – 2,499	< 1,500
WBC Decrease – cell/mm  (African American Males)	2,200 – 2,499	1,200 – 2,199	<1,200
WBC Decrease – cell/mm  (African American Females)	2,200 – 2,499	1,500 – 2,199	<1,500
Neutrophils Decrease – cell/mm 	1,300 – <1,699	1,000 – 1,299	< 1,000
Neutrophils Decrease – cell/mm  (African American Males)	1,000 – 1,299	800 - 999	<800
Neutrophils Decrease – cell/mm  (African American Females)	1,100 – 1,299	1,000 – 1,099	<1,000
Platelets Decreased - cell/mm 	120,000 – <150,000	100,000 – 119,999	<100,000
PT (prothrombin time) – seconds	11.6 – 12.6	12.7 – 13.7	>13.7
PT INR (Prothrombin INR)	1.2-1.4	1.5-1.9	2.0 or higher
PTT (partial thromboplastin time) –seconds	30.1 – 36.8	36.9 – 43.6	>43.6
Total Protein – g/dL	5.5 - 5.9	5.0 - 5.4	<5.0
Alkaline phosphatase – IU/L (Male)	1.1 - ≤ 2.0 x ULN	>2.0 - ≤ 3.0 x ULN	>3.0 x ULN or higher
Alkaline phosphatase – IU/L (Female)	1.1 - ≤ 2.0 x ULN	>2.0 - ≤ 3.0 x ULN	>3.0 x ULN or higher
Hematocrit (Male) - %	33.0 -36.1	29.8 - 32.9	< 29.8
Hematocrit (Female) - %	29.5 - 32.6	26.0 – 29.4	< 26.0
RBC (Male) – x 10  /uL	3.9 - 4.1	3.4 - 3.8	< 3.4

Adverse Events*	Mild (Grade 1)	Moderate (Grade 2)	Severe (Grade 3)
RBC (Female) – x 10  /uL	3.5 - 3.7	3.0 - 3.4	< 3.0
Lymphocytes - cell/mm  decrease	600- 799	500 – 599	< 500
Monocytes – cell/mm  increase	1001-2000	2001-3000	>3000
Eosinophils - cell/mm  increase	871 - 950	951 - 1700	>1700
Basophils - cell/mm  increase	101 - 300	301 - 800	> 800
High Density Lipoproteins (HDL) Male – mg/dL	N/A	N/A	N/A
High Density Lipoproteins (HDL) Female – mg/dL	N/A	N/A	N/A
Total Carbon Dioxide – mEq/L	N/A	N/A	N/A
Total Cholesterol – mg/dL	N/A	N/A	N/A
Low Density Lipoprotein Cholesterol, Direct – mg/dL	N/A	N/A	N/A
Triglycerides – mg/dL	N/A	N/A	N/A
Laboratory Adverse Events* (Urine)			
Protein	1+	2+	>2+
Glucose	1+	2+	>2+
Blood (microscopic) - red blood cells per high power field (rbc/hpf)**	3-10**	11-50**	>50 and/or gross blood**

\*Abnormal laboratory values, performed as part of hematology, chemistry panel, or urinalysis but not listed in Appendix B, VT-1598 TOXICITY GRADING CRITERIA FOR NORMAL HUMAN SUBJECTS, will be evaluated by the study clinicians, recorded in the source document and, if clinically significant, considered AEs and graded according to the criterion described in [Section 8.1](#).

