- UA parameters: specific gravity by dipstick, pH by dipstick, occult blood by dipstick, leukocyte esterase by dipstick. If dipstick urinalysis testing is abnormal, RBC by complete UA and WBC by complete UA will be assessed. Urinalysis WBC count will be measured but the results will not be graded for toxicity.
- VS parameters:
 - VS will be obtained after subjects have rested for at least 5 minutes.
 - VS parameters will be graded according to the toxicity grading criteria in [Table 6](#).
 - Subjects with a history of sinus bradycardia will only have AEs of moderate severity or greater entered for bradycardia/decreased heart rate.
 - The following parameters will be measured:
 - Systolic blood pressure, diastolic blood pressure, pulse, respiratory rate, and temperature.
- ECG parameters:
 - ECG measurements will be conducted in triplicate, and the mean of triplicate values will be used for analysis, including analyses of change from baseline.
 - All ECG triplicate readings will be conducted at least 1 minute apart within a 15-minute period.
 - ECG results will be read by the study PI or a designated clinician and graded according to the toxicity grading criteria in [Table 6](#). For each timepoint, overall interpretation of the ECG will be reported as Normal; Abnormal, Not Interpretable; or Abnormal, Clinically Significant (CS). Evaluation of rhythm, arrhythmia, conduction disturbance, axis, myocardial infarction, ST segment, and other abnormal findings will also be assessed.
 - If QTcF prolongation occurs after dosing then telemetry monitoring will start, and triplicate 12-lead ECGs will be captured every 30 minutes until the average for the triplicates has returned to within 60 ms of the baseline value.
 - The following parameters will be measured:
 - PR interval, QRS duration, QT interval, QTcF interval, RR interval, and mean ventricular heart rate.
 - Prior to 16NOV2020 QTc interval was included in the ECG parameters measured. Because QTc and QTcF are similar intervals, the study team determined that QTc should be removed from the eCRF so as to reduce redundant data collection. QTcF was kept as the interval as it is the parameter referenced in the Inclusion and Exclusion criteria.
- Physical exams:
 - Complete physical exams include the following parameters:

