9.6. Clinical Laboratory Evaluations

Toxicity grading criteria for clinical laboratory results can be found in [Table 4](#). Unscheduled clinical laboratory evaluations will be included in listings of all clinical laboratory results, but excluded from tabular and graphical summaries by timepoint, except when calculating the maximum severity post baseline. Any pre-existing abnormal lab results at Screening and Baseline will be graded and presented in listings but will not be reported as an AE unless it is treatment-emergent (i.e. severity worsens after dosing). Clinical laboratory parameters that have grading criteria for both decreases (result lower than normal range) and increases (result higher than normal range) will be summarized separately by direction. Descriptions of each clinical laboratory summary are described below:

The following laboratory parameters will be presented (in order):

- CHEM: albumin, glucose, blood urea nitrogen, potassium, calcium, sodium, chloride, total protein, creatinine, triglycerides, total cholesterol, LDL cholesterol, HDL cholesterol, total carbon dioxide, creatine phosphokinase, phosphorus, magnesium, GGT, alkaline phosphatase, AST, ALT, total bilirubin, direct bilirubin, and serum cortisol.
- HEM: hemoglobin, hematocrit, lymphocytes, neutrophils, monocytes, eosinophils, basophils, platelet count, RBC, and WBC.
- COAG: prothrombin time, PTT, and international normalized ratio.

- UA: specific gravity by dipstick, pH by dipstick, occult blood by dipstick, leukocyte esterase by dipstick, RBC by complete UA, and WBC by complete UA (microscopic tests to be completed if dipstick urinalysis is abnormal). If microscopic results were obtained in the absence of an abnormal dipstick result (or without dipstick tests being done), results of the complete urinalysis or microscopy will still be summarized.

All safety laboratory results, severity, and change from baseline will be listed for each subject by Dose Group and timepoint. Abnormal laboratory results (laboratory results outside the normal range defined in the MOP) will be presented. Abnormal laboratory results that do not have toxicity grading ranges defined in the protocol will not have severity indicated in tables and listings of abnormal laboratory results, except as “ONR” (out of normal range).

- All CHEM results, including unscheduled visits, will be presented in [Listing 12](#). Abnormal results will be presented in [Table 23](#).

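### Urine protein, urine glucose, amylase and lipase have toxicity grades but no scheduled test, so routine testing cannot grade them and the halting rules would not capture them systematically

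*Protocol*

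**What the plan says.** **What is measured.** The Urinalysis paragraph of Protocol 7.2.1 specifies "urinalysis testing (leukocyte esterase, blood, pH, and specific gravity": four dipstick readings, with microscopy only after an abnormal dipstick. Appendix A footnote h and SAP Table 2 repeat them. SAP 4.5 gives "UA parameters: specific gravity by dipstick, pH by dipstick, occult blood by dipstick, leukocyte esterase by dipstick", and SAP 9.6 presents "UA: specific gravity by dipstick, pH by dipstick, occult blood by dipstick, leukocyte esterase by dipstick, RBC by complete UA" and urine WBC. The chemistry panel in Protocol 7.2.1 ends with "total bilirubin, direct bilirubin and serum cortisol". Neither it nor its counterparts in Appendix A, SAP 4.5 and SAP 9.6 include amylase, lipase or indirect bilirubin.

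**What is graded.** Appendix B has three urine rows: protein (1+, 2+, above 2+), glucose (the same steps) and microscopic blood. It also grades amylase, lipase and indirect bilirubin as multiples of the upper limit of normal (ULN). SAP Table 4 carries all of these rows.

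**What the grades feed.** Laboratory safety is part of the primary outcome (Protocol 3.2.4). The study rule in 8.6.1 and the cohort rule in 8.6.2 count Grade 2 or higher related laboratory or systemic AEs falling in the same MedDRA high-level group term. Exclusion criterion 6 refers to Appendix B for out-of-range laboratory values.

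**The concern.** A grading row works only if some planned test produces a value to grade. For four analytes the plan has cut-offs but no measurement. A subject could have Grade 2 proteinuria or glucosuria that no scheduled test would show, and it would not enter the counts of 2 per cohort or 5 per study. Such findings may cause no symptoms, so nothing would necessarily prompt an extra test.

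The gap also affects eligibility and baseline. Protein and glucose are not read at Screening or Day -1, so a pre-existing abnormality is neither screened out nor recorded.

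The urine rows deserve attention because Protocol 2.3.1 reports "mild to moderate decreases in serum albumin" in animals, together with lower urine pH and specific gravity and higher urine volume. Urine protein and glucose would help interpret such changes if they appeared in subjects. That link is an inference: the protocol reports no proteinuria, glucosuria, or amylase or lipase change in animals.

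**Working it through.** The plan states no figure to reproduce. The check sets the grading tables against the panels and then counts specimens.

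**1. Graded against scheduled.** Collapsing sex, direction and race strata, Appendix B and SAP Table 4 give Grades 1-3 to 36 analytes. Of these, 31 are in a scheduled panel, counting urine red cells, which are read conditionally. That leaves 36 - 31 = 5.

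| Graded analyte | In a scheduled panel? | Obtainable from scheduled data? |
|---|---|---|
| Urine protein | No | No |
| Urine glucose | No | No |
| Amylase | No | No |
| Lipase | No | No |
| Indirect bilirubin | No | Yes: total minus direct, both measured |

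So 5 - 1 = 4 analytes have no routine value. For indirect bilirubin, only the derivation and display are missing.

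**2. Is it a copying slip in one list?** The same four-reading urine panel stands in five places across the two documents. The SAP also converted the amylase and lipase multiples into absolute limits. Dividing its grade limits by the Appendix B multiples recovers a single ULN for each:
- Amylase: 162.8/1.1 = 222/1.5 = 296/2 = 148 U/L.
- Lipase: 73.7/1.1 = 100.5/1.5 = 134/2 = 67 U/L.

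SAP Table 4 therefore holds worked-out limits for tests that the SAP neither schedules nor presents.

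**3. Specimens.** Urinalysis is scheduled at Screening, Day -1 and Days 4, 7, 14 and 21. Planned dosings are 6 cohorts x 8 = 48, of which 6 x 6 = 36 are active.
- Post-dose: 4 x 48 = 192, of which 4 x 36 = 144 are on active drug.
- Pre-dose: 2 x 48 = 96.
- Per cohort, up to Day 7 (Days 4 and 7): 2 x 8 = 16 of 4 x 8 = 32 post-dose specimens.

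**4. Which halting rules are touched.**
- Sentinel rule: ends at Day 3, before the first scheduled post-dose laboratory test on Day 4. Extra dipstick readings would not change it.
- Cohort rule: ends at Day 7, so only the Day 4 and Day 7 specimens could feed it.
- Study rule: runs throughout, so all four post-dose specimens could feed it.

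**5. The urine grade table.** SAP Table 37 is to repeat Table 28, which is restricted to parameters with protocol grading criteria. Its parameter order is specific gravity, pH, leukocyte esterase, urine RBC and urine WBC. Only urine RBC has grades, and SAP 4.5 says urine WBC will not be graded. Four of the five listed parameters cannot be graded, and two of the three graded urine rows are absent.

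**The case against.** **Surplus rows rather than missing tests.** The urine panel is identical wherever it appears, which suggests a deliberate choice. Protocol 7.2.1 says the scale was adapted from an FDA vaccine-trial scale and a DMID table. A grading scale is a reference, not a schedule, and may carry rows for occasional results. This has force for amylase and lipase, where deleting the rows would be a sufficient reconciliation. It has less force for protein and glucose, because they can be read on urine already collected at every laboratory visit.

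**Unscheduled tests.** A reader might infer that these toxicities can never be detected or reach the halting rules. The documents do not support that. Protocol 6.7 lets the investigator obtain any procedure judged necessary, and a resulting Grade 2 or higher related event could count. What remains is that capture depends on discretion. A post-dose result would also have no baseline for the treatment-emergent definition in Protocol 10.5.2.

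**Other monitoring.** Serum albumin, total protein, creatinine, urea nitrogen and fasting glucose are scheduled and graded, so the albumin signal is followed directly. That stands and limits the loss.

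**Size.** Three larger claims are tempting and do not hold:
- Five unmeasured analytes: indirect bilirubin can be derived, so the count is four.
- All 6 x 48 = 288 urine specimens as lost toxicity data: 96 are pre-dose and cannot show a treatment effect.
- A gap in SAP Table 38: that table covers only specific gravity and pH, and SAP 9.6 excludes character results such as 1+ from change-from-baseline summaries.

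**Timing.** SAP section 15 reports in the past tense that one Cohort 3 subject returned for Cohort 6, so much of the urine had probably been processed. This stands, and it shapes the fix.

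**Conclusion.** The mismatch is established from the documents. Four graded analytes are in no scheduled panel, so routine testing yields no baseline or post-dose grade for them, and the related-event halting rules would not capture them systematically. The extent is up to 192 scheduled post-dose urine specimens (144 on active drug) unread for protein and glucose, assuming all 48 planned dosings and complete attendance. Only the Day 4 and Day 7 specimens bear on cohort escalation. Indirect bilirubin is a lesser gap, and Table 37 is misaligned with the scale it is meant to report.

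The documents do not show that any toxicity was missed, that these findings are expected with VT-1598, or that the halting rules fail for other laboratory events. The urine part is more than tidying because it concerns a primary safety outcome in a first-in-human trial and is cheap to correct. The amylase and lipase part is reconciliation only.

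**What to change.** - Read protein and glucose by dipstick on the urine already collected. Add both to Protocol 7.2.1, Appendix A footnote h, SAP 4.5 and 9.6, and the parameter lists of SAP Tables 26, 36 and 37. Leave Table 38 unchanged.
- Limit Table 37 to urine parameters that have grades.
- State that indirect bilirubin is total minus direct, and where it will be shown.
- Reconcile the amylase and lipase rows with the chemistry panel: measure them on the existing sample or remove the rows from both grading tables.
- For specimens already processed, list any protein or glucose results the laboratory recorded. Otherwise state in the CSR that these graded parameters were not assessed, so that an absence of events is not read as a negative result.

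The cost is two further readings on an existing specimen plus wording changes, with no added visit, blood draw or subject. The downside is a few incidental low-grade dipstick findings to review.
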